Initial contact and interview: The initial contact will include a brief interview to cover inclusion/exclusion criteria and a brief description of the study will be given to the patient to determine if the patient is interested in participating. If the patient is interested then an informed screening consent will be signed by the patient and witnessed by a member of the research staff.

Medical aspects: Patients will receive a full physical examination and an ECG before admission. Laboratory tests will include: hematology, blood chemistry (including liver function tests), urinalysis, and blood pregnancy test for women (45 minutes). Urine will be collected and tested for substances of abuse, three times a week for the duration of the study.

Demographic information: Patients will complete a Demographic Form, Medical and Psychiatric History Form, and Family Medical and Psychiatric History Form. These self report forms provide data on age, race, socioeconomic status, marital status, educational and occupational levels, significant medical history, and current/history of major psychiatric disorder in the patient and his/her first degree relatives. Patients will also complete a Locator Form so that they can be contacted for follow-up (30 minutes).

c. Screening and Diagnosis: Uniform screening procedures will be used. A standardized telephone interview is followed by an appointment for those who meet general study criteria. No identifying information is recorded until the potential participant completes the study explanation and consent process; evaluation follows consent using standardized measures. Common, standardized intake and evaluation training will be conducted for all procedures and instruments.

Eligibility Determination via Physical Examination and Psychiatric Evaluation: Review of history, physical, and laboratory evaluations and the medical-psychiatric evaluation note lead to final determination of eligibility. This information will be reviewed by the study psychiatrist trained in the protocol.

NEW YORK STATE PSYCHIATRIC INSTITUTE INSTITUTIONAL REVIEW BOARD

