Study: # 6850 entitled A sequenced behavioral and medication intervention for cocaine dependence

PI: [name]

NCT# NCT01986075

Statistical Analysis Plan created on Date: 7/05/2012

export data files that are easily read by statistical software packages.

**C7. Data Analysis:** [name], a Biostatistics Faculty member assigned to our division, has extensive experience in the analysis of clinical trial data and will design and oversee all analyses. The primary analyses in this study will be on the intent-to-treat (ITT) sample, (i.e. on all 100 randomized patients). Prior to conducting hypotheses testing we will examine all variables for the presence of outliers and deviations from normality, and transformations will be employed, if necessary. The distribution of demographic variables (ethnicity, sex, age) will be examined and described in terms of means, standard deviations, proportions and 95% confidence intervals. [Demographic and baseline clinical variables will also be examined as predictors of the primary outcome measure, and those found to be significant will be considered as covariates.]

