**C9.** Intent to Treat/ Dropouts and missing data: The primary analyses will be on the Intent-to-treat (ITT) sample, (i.e., all randomized subjects according to the treatment they were assigned). We will account for dropouts by examining the primary outcome variables using (longitudinal) mixed effects models (MEM) (Brown and Prescott 1999; Diggle et al 2002) using PROC GLIMMIX in SAS®. MEMs do not require a complete set of time points to estimate the outcome variable. However, inferences from analyses with missing data are valid provided that the data are "missing at random" (Little and Rubin 1987). While 'missing at random' (i.e, the missing mechanism does not depend on the value of the unobserved outcome) is un-testable in most medical research, parametric or semi-parametric models (that both depend on the unobserved outcome value) can be used to model the missingness (Diggle and Kenward 1994; Kenward 1998; Liu et al 1999; Rotnitzky et al 1998; Scharfstein et al 1999). Comparisons of the inferences from the various models of missingness provide a measure of the validity of the 'missing at random' assumption. One can also compute a local sensitivity index which measures the change in the estimated treatment effect in a neighborhood of the 'missing at random' model (Rotnitzky et al 2001). We plan to perform a *sensitivity analysis* based on these two approaches to assess the effect of the assumption of missing 'at random' on the inference.

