**C10. Primary Outcome Measures:** The primary outcome measure will be a binary indicator (yes or no) of at least 3 weeks of urine toxicology confirmed self-reported abstinence during Phase-2 (weeks 5-14). While the standard method for measuring cocaine use outcomes is urine toxicology, self-reported cocaine use confirmed by urine toxicology provides additional data that cannot be determined by laboratory testing alone. The reliability of self-reported cocaine use in the context of confirmatory urine toxicology testing is high; for example among 121 cocaine-dependent outpatients self-report matched the toxicology results 94% of the time (Carroll, et al., 2004). Self-reported cocaine use data will be collected using the timeline followback method for the 28 days preceding study entry and each day of the study period. Semi-quantitative urine benzoylecgonine (BE) levels will be obtained with Abbot/ADX technology. To prevent overestimation of cocaine use, we will confirm self-reported cocaine use with a modified version of a procedure developed by (Winhusen et al. 2007), a procedure we have employed in previous studies (e.g. [name] et al., in press). Self-report of cocaine use will be accepted as a "use day" and urine samples with BE levels equal to or greater than the standard NIDA 300 ng/ml will be considered positive. A urine sample will be considered negative if it is preceded within two days by a sample with 2x or more its BE level. If none of the three days preceding a positive urine sample has been self-reported as a use day, the day immediately preceding the sample will be labeled a use day.

Primary hypothesis: A greater proportion of patients treated with CRA+CM/MAS-ER will achieve continued abstinence compared to patients treated with CRA+CM/PLACEBO. The effect of treatment on the

Research Strategy Page 101

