outcome (at least 3 consecutive weeks of urine toxicology confirmed self-reported abstinence) will be examined using logistic regression adjusted for covariates (e.g., baseline days/week of cocaine use):  $logit(Y_{ikt}) = \beta_0 + \beta_1 I_{ij}^M + \beta_2 Z_{ijk} + e_{ijk}$ ; where  $Y_{it}$  is a binary outcome indicating 3 weeks of abstinence ( $Y_{itk} = 1$ , when a given individual in a treatment condition is abstinent),  $I_{ij}^M$  is an indicator for the medication treatment ( $I_{ij}^M = 1$  for MAS-ER and  $I_{ij}^M = 0$  for PLACEBO), ),  $Z_{ijk}$  is a vector of covariates, such as baseline cocaine use, and demographic characterisitics (age, gender, ethnicity), and  $e_{ijk}$  is random error. [Covariate by treatment interactions will be tested for significance and the main effect, the primary hypothesis will be answered by testing the null hypothesis  $B_1=0$ . ]

- **[C11. Predicting Responder and Non-Responder status.** Analyses will be conducted to identify variables that may help predict who is more or less likely to respond to the psychosocial intervention alone. Identifying key cognitive-verbal mechanisms (see below) that predict treatment response can help provide important avenues for guiding future therapy development. This important aim will be examined using a logistic regression model within a general linear model framework where responder status at the end of week 4 is a binary outome and the predictors will be a vector of baseline covariates. Predictor variables will be entered in blocks and tested for significance (baseline commitment language, executive functioning, implicit cognition, coping skills, baseline cocaine use, and demographic characteristics (age, gender, ethnicity). Furthermore, a vector of variables representing the magnitude of change in the cognitive, behavioral, and verbal mechanisms will be tested. This later block of variables will evaluate if the response to the behavioral intervention alone is predicted by the magnitude of change in the key cognitive, verbal, and behavioral indices.]

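### C10's primary logistic test needs a fixed covariate set, a named test and a dropout rule; C9's longitudinal model does not fit a single yes/no outcome

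*SAP*

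**What the plan says.** - **Outcome (SAP C10).** "The primary outcome measure will be a binary indicator (yes or no) of at least 3 weeks of urine toxicology confirmed self-reported abstinence", counted over weeks 5-14: one value per patient.
- **Model (SAP C10, primary hypothesis).** A "logistic regression adjusted for covariates (e.g., baseline days/week of cocaine use"). The covariate term "is a vector of covariates, such as baseline cocaine use, and demographic characterisitics (age, gender, ethnicity"). The printed equation has treatment and covariates and no interaction term.
- **Interactions (SAP C10).** "Covariate by treatment interactions will be tested for significance and the main effect, the primary hypothesis will be answered by testing the null hypothesis", the null here being B1=0. No order, threshold or consequence is given.
- **Covariate screen (SAP C7).** Patient characteristics at entry, both demographic and clinical, "will also be examined as predictors of the primary outcome measure, and those found to be significant will be considered as covariates". There is no closed candidate list and no threshold.
- **Dropouts (SAP C9).** "We will account for dropouts by examining the primary outcome variables using (longitudinal) mixed effects models (MEM"), in PROC GLIMMIX. C9 keeps the sensitivity label for later checks of the missing-at-random assumption.
- **Data before randomisation.** Timeline follow-back is collected "for the 28 days preceding study entry and each day of the study period" (SAP C10). "Urine will be collected and tested for substances of abuse, three times a week for the duration of the study" (Protocol, Treatment Study Screening Procedures). Randomisation follows week 4 (Protocol, Design Overview). Use in weeks 1-4 is not named as a covariate in the primary model.

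**The concern.** A primary analysis should be reproducible from its text. Here the model type and the null hypothesis are given, but four things that affect the p-value are left to the analyst: which covariates enter, what a significant interaction leads to, which test of B1 is used, and how a patient who leaves early is scored. The last matters most for the logic of the plan. The only method given for dropouts in the primary analysis is a longitudinal model, and C10's outcome has no repeated values to model. To use it, the analyst would have to replace the outcome with something measured weekly.

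There is also a missed opportunity. Baseline use appears to mean use at study entry, since C13 separates Baseline from Week 5. Use in weeks 1-4 lies nearer the outcome period and is fully recorded before randomisation.

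**Working it through.** **1. The plan's own power (SAP C8).** Inputs: p1 = 0.37, p2 = 0.10, two-sided alpha 0.05 (sidedness assumed), mean rate 0.235. Pooled formula: power = Φ{[0.27√n − 1.96√(2×0.235×0.765)] / √(0.37×0.63 + 0.10×0.90)}.
- n = 50: Φ{(1.909 − 1.175)/0.568} = Φ(1.29) = 90.2%. C8 states 90%.
- n = 34: Φ{(1.574 − 1.175)/0.568} = Φ(0.70) = 75.9%. The unpooled formula gives 79.1% and the exact chi-square 78.7%. C8 states 80%, so it is reproduced to within 2 points on these last two.

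These are unadjusted comparisons of two proportions. They do not settle which covariates or which test C10 uses.

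**2. C9 beside C10.** C10 yields one yes/no value per patient. A longitudinal mixed model needs repeated values per patient. It could be fitted to weekly use, but weekly urine results are a secondary outcome in C12. So C9's model cannot supply the C10 result, and C10 has no scoring rule for dropout. The Protocol counts a missed specimen as positive, but only within the contingency-management procedures.

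**3. Room for covariates.** Expected responders at 50 per arm: 50×0.37 + 50×0.10 = 23.5. Treatment plus two covariates: 23.5/3 = 7.8 per term. Treatment plus C10's named examples (use, age, gender, ethnicity): 23.5/5 = 4.7.

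**4. The C7 screen.** Applied as one fixed rule to five candidates (2,500 simulated trials, 20% null rate, 34 or 50 per arm), type I error is 4.9-6.5%. The screen alone barely changes error rates.

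**5. Wald or likelihood-ratio.** Treatment plus two use covariates (correlation 0.5), 6,000 trials per cell. Assumed log odds ratios per SD: none; moderate (−0.5 each); strong (−0.5 and −1.0).

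| Setting | Wald | Likelihood-ratio |
|---|---|---|
| 50/arm, null 10% | 2.9-3.0% | 6.3-6.8% |
| 50/arm, null 20% | 4.6-4.9% | 5.6-5.9% |
| 50/arm, 37% vs 10% | 90.0-94.7% | 91.5-95.9% |
| 34/arm, 37% vs 10% (moderate, strong) | 76.0%, 80.2% | 82.4%, 86.1% |

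A second simulation, randomising only week-4 non-responders, agrees. At 34 per arm the tests disagree in about 6% of trials (power 72-77% against 78-84%). At 50 per arm with a 10% null, type I error is 2.5-3% against about 6%.

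**6. Adding weeks 1-4 use.** Randomised patients are taken as the top 100/155 = 64.5% on weeks 1-4 use; slope 0.5, 1.0 or 1.5 per SD; likelihood-ratio test; 50 per arm; 37% vs 10%; 3,000 trials. Power with entry use / entry use plus demographics / entry plus weeks 1-4 use:
- correlation 0.3: 92.4/92.6/92.7, 91.6/91.4/92.6, 91.8/91.4/94.4
- correlation 0.5: 91.3/90.9/91.7, 90.9/90.8/92.0, 91.1/90.7/93.5
- correlation 0.7: 90.5/90.3/90.7, 91.5/91.0/92.6, 93.3/92.4/94.4

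The gain is 0.2 to 2.6 points over entry use alone and 0.1 to 3.0 over entry use plus demographics. A further simulation (non-responders only, correlation 0.5) gave −0.4 to +1.5 points at 50 per arm and −0.6 to +2.3 at 34 per arm. If neither use covariate is prognostic, adjusting for both costs 90.2 − 90.0 = 0.2 points at 50 per arm and 73.6 − 72.8 = 0.8 at 34 per arm against no adjustment (Wald).

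**The case against.** The strongest reply is that the primary test is not really in doubt. Under its primary hypothesis C10 names logistic regression, prints a main-effects equation and ties the answer to B1=0. C9 sits under a heading about dropouts. All of that stands: this is loose text around a valid test, not two rival primary analyses of equal standing. What survives is that C9 does not present its mixed model as a sensitivity analysis, and that setting it aside leaves no dropout rule.

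A reader might infer more. The documents do not support these readings:
- **That the plan gives conflicting primary results.** Setting a weekly mixed model against C10's logistic model gives disagreement on significance in 33-40% of simulated trials at 25% vs 10%. That compares two different outcomes, at rates the plan does not use; at the planned 37% vs 10% it is 9-10%. Type I error of 6-10% (logistic alone 2-5%) needs an analyst free to report either.
- **That interactions inflate the error rate.** At a 23.5% null rate, keeping significant uncentred interactions gives 13.8%, against 5.1% for main effects and 5.2% if centred. This needs two steps that no passage states: retaining the term and leaving covariates uncentred.
- **That omitting weeks 1-4 use is an error.** The test is valid without it. Restricting randomisation to non-responders also narrows the covariate and may weaken it.

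**Conclusion.** The point holds as a should-fix on specification, with medium confidence. The primary test is identifiable, but its covariates, the role of interactions, the test statistic and the scoring of dropouts are not fixed, and C9's model does not match C10's outcome.

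The size that can fairly be attached is modest. The unnamed test is worth about 6 power points at 34 per arm and moves type I error between roughly 3% and 6% at 50 per arm when the null rate is 10%. The C7 screen matters little. Weeks 1-4 use adds about 0 to 3 points at 50 per arm, and near zero if it is not prognostic. The documents give no prognostic strength or correlation, so all covariate results rest on the assumed ranges shown. The effect of the missing dropout rule cannot be sized here, because the documents give no dropout rate for the randomised phase.

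**What to change.** Amend the SAP before unblinding:
- **Primary test.** The primary p-value is the test of B1=0 in C10's main-effects logistic model, in all randomised patients. Name Wald or likelihood-ratio.
- **Covariates.** Exactly two: entry use (days per week, timeline follow-back, 28 days before entry) and weeks 1-4 use (use days before randomisation, by C10's self-report-plus-urine procedure). State the rule for missing days, including which days a urine sample is taken to cover.
- **Dropouts.** State how they are scored in the binary outcome; for example, not abstinent unless 3 consecutive confirmed weeks had already been reached.
- **C7.** Delete the significance screen.
- **Interactions.** Report them only in separate exploratory models with centred covariates, with no effect on the primary test.
- **C9.** Label the weekly mixed models as sensitivity analyses.

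The cost is SAP wording. Weeks 1-4 already supply 28 days of timeline follow-back and 3×4 = 12 scheduled urines per patient, so no patients, visits or assays are added. What is given up is later choice of covariates and model.

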- [C12. Secondary hypotheses and outcomes: Patients receiving CRA+CM/MAS-ER will demonstrate a greater reduction in cocaine use, cravings, and withdrawal symptoms, increased retention and quality of life compared to patients treated with CRA+CM/PLACEBO. Analyses will test the hypotheses that the CRA+CM/MAS-ER group will demonstrate 1) a lower proportion of weekly urine toxicology samples testing positive for benzoylecgonine (longitudinal continuous variable); 2) lower cocaine withdrawal symptoms as measured by the Cocaine Selective Severity Assessment (CSSA; a longitudinal continuous variable), 3) lower cocaine craving as measured by the Cocaine Craving Questionnaire (longitudinal continuous variable) 4] better quality of life (Endicott et al., 1993), and 5) greater study retention then the PLACEBO/CRA+CM group. The longitudinal continuous outcomes will be treated with longitudinal mixed effect models (MEM), where patients will be treated as a random factor. Appropriate transformations of distributions will be applied to the outcome variable if needed (for count variables, the Poisson distribution will be used). The group differences in retention is operationalized as time to dropout, which will be analyzed within a Cox proportion hazard framework. **Exploratory Analyses:** We will also test for differences in treatment outcome between the CRA+CM only condition (no medication or placebo) and each of the medication treatment arms (CRA+CM/MAS-ER and CRA+CM/PLACEBO) on the primary and secondary outcomes outlined above. Recall, this group will consist of the individuals who responded to the behavioral treatment during the 4-week run-in and were not randomized to receive either MAS-ER or PLACEBO. These exploratory comparisons will provide useful information on the relative differences between individuals needing an integrative treatment strategy against those benefiting from the behavioral treatment alone in terms of their trajectory and level of change during a treatment episode.

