
C14. Exploratory Analyses. A series of analyses will also be conducted to investigate the effect of each treatment condition on the key cognitive domains assessed and coping skills over time. The analysis of secondary outcomes collected over time will be based on Mixed Effect Models (MEM) for longitudinal data (Diggle et al., 2002). MEM requires no parametric distributional assumptions, provides robust inference with respect to misspecification of the covariance, and allows for the analysis of continuous, categorical and count data which may be missing for some patients either because of a missed week or due to drop-out, thus complete information for all patients is not needed. PROC NL MIXED or GLIMMIX in SAS will be used to carry out these analyses. The analyses will be used to separately test the effect of treatment condition on the magnitude of change between week 5 and week 14 for each the cognitive functioning domains and coping skill acquisition factors. Treatment condition and treatment by time interaction terms will be entered as predictors. This approach is potentially more sensitive to treatment effects since it incorporates each measurement period and effects of time. A treatment effect would be reflected in a significant main effect of either treatment or treatment by time interaction. If appropriate, baseline level of cocaine use will also be included as a covariate to test if it moderates the effect of treatment on the cognitive and behavioral outcome measures.

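### SAP C12 does not commit to adjusting each longitudinal secondary outcome for the patient's own pre-randomisation value, which may give up precision in otherwise valid comparisons

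*SAP*

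**What the plan says.** SAP C12 opens with a hypothesis about change: "Patients receiving CRA+CM/MAS-ER will demonstrate a greater reduction in cocaine use, cravings, and withdrawal symptoms". The individual tests listed under it are worded as differences in level, for example "a lower proportion of weekly urine toxicology samples testing positive for benzoylecgonine (longitudinal continuous variable". The model is then described: "The longitudinal continuous outcomes will be treated with longitudinal mixed effect models (MEM), where patients will be treated as a random factor". C12 allows transformations and a Poisson model for counts. It does not list fixed effects, covariates or the weeks analysed, and it does not say whether values from before randomisation enter at all.

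Three other SAP sections come near the point, but none settles it:

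- **C7** has a covariate rule, but it screens against the primary outcome: "Demographic and baseline clinical variables will also be examined as predictors of the primary outcome measure".
- **C10** adjusts the primary logistic model for covariates and gives baseline days per week of cocaine use as an example. It does not carry this over to C12.
- **C14** has a general sentence, "The analysis of secondary outcomes collected over time will be based on Mixed Effect Models (MEM) for longitudinal data", and adds "Treatment condition and treatment by time interaction terms will be entered as predictors". Its only baseline covariate is conditional and serves as a moderator: "If appropriate, baseline level of cocaine use will also be included as a covariate to test if it moderates the effect of treatment". The outcomes it names are cognitive domains and coping skills.

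The protocol does provide pre-randomisation data. Under Assessment Instruments (Medical aspects): "Urine will be collected and tested for substances of abuse, three times a week for the duration of the study". Randomisation follows four weeks of behavioural treatment. The Cocaine Selective Severity Assessment, the Brief Substance Craving Scale and the quality-of-life questionnaire are all described with the intake evaluation.

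**The concern.** In repeated measures on cocaine users, much of the variation lies between patients and is already visible before randomisation. A patient random effect accounts for the correlation among a patient's own weeks. If only post-randomisation rows are analysed, it does not remove the between-patient part from the treatment contrast. A covariate measured before the first capsule removes some of it.

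Two things are at stake. The first is precision, with about 50 patients per arm on five secondary hypotheses. The second is prespecification. C12 leaves open an analysis of post-randomisation levels, of change scores, or of levels adjusted for the earlier value. These can differ a good deal in power, and the choice should be fixed before the data are seen.

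**Working it through.** **Inputs**

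- Randomised patients: 100 (SAP C7). I take 50 per arm, the larger of the two sizes in C8.
- Post-randomisation weeks: 5 to 14, so 10 weekly values. C10 states this window for the primary outcome; C12 states none.
- Scheduled urines before randomisation: 3 per week × 4 weeks = 12.
- Correlation between the pre-randomisation value and later values: not in the documents. I assume 0.3 to 0.7.
- Alpha 0.05, taken as two-sided because the SAP does not say.

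**The plan's own figures.** There is none for the C12 outcomes. C8's figures concern the primary outcome (37% vs 10%: 80% power with 34 per arm, 90% with 50). The unpooled normal formula, Φ(0.27/√((0.37×0.63 + 0.10×0.90)/n) − 1.96), gives 79.1% and 91.9%. They reproduce closely but have no bearing on C12.

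**Step 1: gain for a given r.** Let r be the correlation between the pre-randomisation value and the weeks 5-14 mean. In a linear model, adjustment multiplies the variance of the treatment contrast by 1 − r². The equivalent sample-size factor is 1/(1 − r²). A test with 50% power moves to Φ(1.96/√(1 − r²) − 1.96). The 50% start is only a reference point.

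| r (assumed) | 1 − r² | Variance falls by | Equivalent extra patients | 50% power becomes |
|---|---|---|---|---|
| 0.3 | 0.91 | 9% | 10% | 54% |
| 0.5 | 0.75 | 25% | 33% | 62% |
| 0.7 | 0.51 | 51% | 96% | 78% |

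**Step 2: the same gain from single-occasion correlations.** Let every pair of occasions correlate at ρ. The mean of 10 weekly values then has variance V = (1 + 9ρ)/10 in SD² units, and V − ρ² after adjustment. The implied r is ρ/√V. The effect detectable with 80% power is (1.96 + 0.84) × √(2 × variance/50).

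| ρ (assumed) | V | V − ρ² | Ratio | Implied r | Detectable effect, SD |
|---|---|---|---|---|---|
| 0.2 | 0.28 | 0.24 | 0.86 | 0.38 | 0.30 to 0.27 |
| 0.3 | 0.37 | 0.28 | 0.76 | 0.49 | 0.34 to 0.30 |
| 0.5 | 0.55 | 0.30 | 0.55 | 0.67 | 0.42 to 0.31 |
| 0.7 | 0.73 | 0.24 | 0.33 | 0.82 | 0.48 to 0.27 |

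The two tables agree: each ratio equals 1 − r² for the implied r.

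**Step 3: is the test on levels valid?** A simulation used 4000 trials per setting, 50 per arm, 10 weekly values and a constant true effect of −0.42 SD. All three analyses estimated about −0.42. With no true effect, all three rejected in close to 5% of trials. Power was:

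| ρ | Post-randomisation levels only | Change score | Levels adjusted for the earlier value |
|---|---|---|---|
| 0.3 | 93% | 66% | 97% |
| 0.5 | 80% | 81% | 96% |
| 0.7 | 69% | 95% | 99% |

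The three analyses target the same effect and differ only in precision. The adjusted analysis has the highest power in each row.

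**The case against.** The best defence is that C12 is silent, not that it rejects adjustment. It lists no fixed effects at all. If pre-randomisation values were entered as response rows, a mixed model would use them. C14's general sentence on secondary outcomes could be read as covering C12, and C7 does not say that covariates chosen by its screen stay in the primary model. All of this is fair, so the point is one of under-specification. Yet on the most generous reading, neither C7 nor C14 guarantees an adjustment for the outcome's own earlier value. C14 offers only baseline cocaine use, and only conditionally.

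Two stronger readings are tempting, and the documents do not support them.

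- A reader might infer that the hypothesis of a larger reduction goes untested because the listed tests compare levels. Randomisation makes the expected arms equal beforehand, so the expected difference in level equals the expected difference in change. The simulation shows the same.
- A reader might also infer that chance imbalance biases the unadjusted result. With 50 per arm, the standard error of a baseline mean difference is √(2/50) = 0.2 SD. An imbalance of 0.2 SD is therefore a one-standard-error event that the unadjusted standard error already reflects.

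Four limits on the size and reach of the gain also stand:

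- Only patients who have not responded by week 4 are randomised. Urine positivity in weeks 1-4 may therefore vary little, which would lower r for that outcome.
- The factor 1 − r² is for linear models and is approximate if a Poisson model is used.
- C12 names the Cocaine Craving Questionnaire, whereas the protocol describes the Brief Substance Craving Scale. The visit schedule is not shown, so week-4 scale values cannot be confirmed.
- C12 does not label quality of life a longitudinal continuous variable, so placing it in the mixed model is an inference.

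**Conclusion.** The point holds as a gap in specification that may cost precision. No section commits to adjusting a C12 outcome for its own pre-randomisation value, although weeks 1-4 urines and the intake scales provide one. If only post-randomisation values are analysed, the comparisons are valid and answer the stated hypothesis, but with more variance than necessary. The reduction available is 9% to 51% for r between 0.3 and 0.7. That range is assumed, and urine may sit at its low end. The primary analysis is not affected.

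**What to change.** In SAP C12, state that values from weeks 5-14 are the response and that each model includes the patient's own pre-randomisation value as a covariate:

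- **Urine:** the proportion of samples positive in weeks 1-4.
- **Withdrawal, quality of life and craving:** the last value before the first capsule, otherwise the intake value.

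For craving, first reconcile the Cocaine Craving Questionnaire (SAP C12) with the Brief Substance Craving Scale (Protocol, Assessment Instruments), so that the baseline and the outcome come from the same instrument. It would also help to name the time and treatment-by-time terms and the contrast that decides each hypothesis.

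The cost is one SAP sentence and one degree of freedom per model. No new data collection is needed; for craving, this assumes that the outcome is settled on the scale already given at intake.

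### SAP C14 credits its mixed models with robustness that a default NLMIXED or GLIMMIX fit does not have, and no residual covariance or standard-error method is specified for weekly outcomes

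*SAP*

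**What the plan says.** SAP C14 sets the method broadly: "The analysis of secondary outcomes collected over time will be based on Mixed Effect Models (MEM) for longitudinal data". It then credits the method with two properties: "MEM requires no parametric distributional assumptions, provides robust inference with respect to misspecification of the covariance". The software follows: "PROC NL MIXED or GLIMMIX in SAS will be used to carry out these analyses".

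The secondary outcomes are listed in C12. One is the weekly proportion of urine samples positive for benzoylecgonine, treated as continuous. C12 describes the models as "longitudinal mixed effect models (MEM), where patients will be treated as a random factor", and adds that "for count variables, the Poisson distribution will be used". No residual correlation structure, random slope, empirical (sandwich) standard error or overdispersion check is stated in C9, C12 or C14. The sensitivity analyses in C9 concern the missing-at-random assumption only.

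On testing, C14 says: "A treatment effect would be reflected in a significant main effect of either treatment or treatment by time interaction". That rule appears where C14 discusses cognitive and coping measures and their change between weeks 5 and 14.

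**The concern.** Both named procedures fit a model with a chosen distribution and random-effect structure. Unless an empirical option is requested, their standard errors are correct only if that structure is correct. Robustness to a wrong covariance belongs to sandwich standard errors, usually met in marginal (GEE-type) methods. C14 therefore claims a property that the plan does not arrange, and its claim of no distributional assumption conflicts with the Poisson specification in C12. C9 meanwhile defends the same class of model under missing at random, an argument that relies on a correctly specified likelihood.

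What is at stake is the test of treatment by time on outcomes measured at many visits. Values from neighbouring weeks are usually more alike than values far apart. A random intercept alone gives every pair of weeks the same correlation. If that is wrong, the model-based standard error of a time trend can be too small, and an analyst who relied on C14 would have no stated reason to look.

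**Working it through.** **Plan's own figure.** The plan gives no error rate for these models. Its only power figures for the randomized comparison concern the primary outcome (C8). The 50-per-arm figure reproduces: 37% against 10%, two-sided 0.05, gives 90.2% against the stated 90%. Here it serves only to fix the sample size.

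**Inputs from the documents.** 100 randomized patients (C7), so 50 per arm; weeks 5 to 14 (C10), so 10 weekly values; patient as a random factor (C12).

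**Assumptions.** Random intercept only; model-based standard errors; AR(1) residual correlation ρ of 0.3, 0.5 or 0.7; no true treatment effect; two-sided 5% test. The documents give no within-patient correlation.

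**Linear time slope.** Let R be the residual correlation matrix over T = 10 weeks, t the centred week (−4.5 to 4.5) and C the matrix that subtracts the patient mean. For balanced data,

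- A = t′Rt / t′t (true variance of the slope, scaled)
- B = trace(CR) / (T − 1) = 1 − mean off-diagonal correlation (what the model uses)
- true SE / model SE = √(A/B)
- type I error = 2Φ(−1.96 / ratio)

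The intercept variance and the number of patients cancel. At ρ = 0.5: A = 1.895, B = 0.822, ratio = √2.305 = 1.52, error = 2Φ(−1.29) = 19.7%.

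**Half the residual variance independent.** Replace R by 0.5R + 0.5I. At ρ = 0.5: A = 0.5(1.895) + 0.5 = 1.448, B = 0.5(0.822) + 0.5 = 0.911, ratio 1.26, error 12%.

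**Week as categorical.** The 9-degree-of-freedom Wald statistic is a weighted sum of χ² variables, with weights equal to the nonzero eigenvalues of CRC divided by B. It is compared with the 5% point of χ² on 9 degrees of freedom.

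| ρ | A | B | SE ratio, linear | Error, linear | Error, linear, half independent | Error, week categorical |
|---|---|---|---|---|---|---|
| 0.3 | 1.499 | 0.918 | 1.28 | 12.5% | 9% | 6% |
| 0.5 | 1.895 | 0.822 | 1.52 | 19.7% | 12% | 8% |
| 0.7 | 2.140 | 0.649 | 1.82 | 28.0% | 16% | 10% |

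**Compound symmetry.** A = B, so the ratio is 1.00 and the error stays at 5%.

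**Two time points (weeks 5 and 14).** A = B = 1 − ρ, so the ratio is 1.00.

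**Simulation check.** 2,000 null trials per scenario, 50 per arm, 10 weeks, random-intercept REML, linear time:

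- Treatment by time, model-based errors: 20.7% at ρ = 0.5 and 27.5% at 0.7. With an assumed 4% dropout per week: 18.8% and 29.7%.
- Treatment by time, sandwich errors on the same fit: 4.8% to 6.1% over ρ = 0.5 to 0.9, with and without dropout.
- Time-averaged treatment effect, model-based errors: 4.6% to 6.0% in every scenario.

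A separate matter is that accepting either of two terms rejects about 10% of the time under the null even when the covariance is right (9.7% to 10.0% simulated). That is not part of the inflation above.

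**The case against.** The strongest reply is that the large figures combine pieces from different analyses. The rule accepting either term is written for cognitive and coping measures, where C14 tests change from week 5 to week 14. With two time points there is no inflation, and adding baseline as a third raises the standard-error ratio to at most about 1.04. C12, which defines the weekly urine outcome, names no treatment-by-time test, and its hypotheses can be read as time-averaged comparisons, which hold their level. This stands. The link runs only through C14's general sentence on secondary outcomes over time, so the consequence is conditional on such a test being run.

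It is also fair that the SAP never says time is linear. A weekly proportion from about three urines also carries independent sampling noise. Both lower the error, as the table shows. Only the urine outcome is documented as weekly: the assessment schedule (Table 3) is an attachment not in these documents, and C12 gives no frequency for craving or withdrawal.

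Finally, naming patient as a random factor excludes neither a random slope nor a residual structure, and C7 has a biostatistician design and oversee the analyses. A reader might infer that the plan has chosen to ignore serial correlation, or that its wording would prevent anyone checking. The documents support neither. They show a missing specification.

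None of this rescues the sentence itself, which attributes to the models properties they lack by default and disagrees with C12.

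**Conclusion.** The point holds as a minor one, limited to secondary and exploratory analyses. The C14 statement is incorrect for the procedures named, and nothing else in the SAP supplies the robustness it claims.

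The possible consequence is a treatment-by-time test on weekly data running at about 12% to 28% (linear time, AR(1) 0.3 to 0.7), about 9% to 16% if half the residual variance is independent, about 5% to 10% with categorical week, and 5% under compound symmetry. These figures rest on a random-intercept fit with model-based errors and on assumed correlation, time coding and variance split.

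A reader might go further and conclude that false positives on the secondary outcomes are likely, or that standard errors are too small for all longitudinal results. The documents do not support that. The time-averaged treatment effect and the week 5 to week 14 comparisons are not materially affected. The C10 primary analysis is a logistic regression on one yes/no result per patient, so it has no repeated measures for this problem to act on.

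**What to change.** Delete the C14 sentence, or correct it to say that the models assume a stated distribution and covariance and that robustness comes from the standard-error method. For each longitudinal outcome, state the distribution and link. For weekly outcomes tested over time:

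- state a residual covariance structure that allows serial correlation, for example AR(1) plus the patient effect;
- use GLIMMIX with small-sample-corrected empirical standard errors, patient as subject;
- say whether week is linear or categorical, and whether treatment by time is a test of interest for the C12 outcomes.

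The two model choices do different work. A better covariance structure supports the missing-at-random argument in C9, and the empirical standard error protects the tests if that structure is still wrong.

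The cost is a short SAP edit and a program option, with no change to data collection or sample size. Confidence intervals will usually be somewhat wider.
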